### III. Preliminary Studies/Progress Report:

**Preliminary Studies.** In a cohort of 652 patients who had undergone surgery at UCH Metro clinicians chose the same cumulative opioid dose (300 oral morphine equivalents) in more than 75% of patients for the discharge opioid prescription (Figure 1). These data indicate that opioids following inpatient surgery are not prescribed in an individualized fashion, but rather that most patients receive a very similar regimen for post-discharge pain management. Using the same EHR (Epic) database that generated the data above, we are able to generate information on types and doses of pain medications that are administered to patients, who are still in the hospital in real time ([name], Chief Medical Information Officer and [name], CMO at UCHHealth strongly support this project). We have previously shown that 83% of patients after Cesarean section and 71% of thoracic surgery patients report taking half or less of opioids prescribed; 53% and 45% respectively report taking five or less of the prescribed pills. Hence, a “one size fits all” approach to pain management after discharge is common in clinical practice and leads to frequent over-prescription of opioids. Based on our own preliminary data and recommendation published by others, opioids taken 24 hours prior to discharge inform the amount of opioids that are likely to be used at home and hence the following prescriptions amounts have been suggested for patients taking equal or less than 22.5 MME in the 24 hours prior to discharge:

[figure not shown]

Figure 4: Cumulative opioid dose in oral morphine equivalents (OME) prescribed to 652 patients upon hospital discharge after surgery. Clinicians chose the same cumulative opioid dose (300 OME) in more than 75% of patients.

- no opioids for home use for patients having taken no opioids in the last 24 hours prior to discharge
- 75 morphine milligram equivalent (MME), e.g. 10 oxycodone 5mg tablets, for home use for patients having taken equal or less than 22.5 MME, e.g. 1-3 oxycodone 5mg tablets in the last 24 hours prior to discharge.

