## **B. Description of Population to be Enrolled:**

### **Survey population:**

Inflating enrollment by approximately 25% to account for drop out and result in 44 patient completers, we will consent 60 adult patients receiving a Cesarean section procedure. After completing an observational study in three surgical groups (thoracic surgery, gastrointestinal surgery, C-section), we chose to evaluate this intervention first in C-Section patients based on their unique characteristics: low procedural variability, low incidences of chronic opioid use, and low level of comorbidities. Also, the issue of having potentially unsecured opioids in a household with young children is of special relevance for opioid safety research in the Cesarean section cohort.

Inclusion Criteria: 1) Women ages at least 18 years of age having undergone Cesarean section surgery at the University of Colorado Hospital are eligible. 2) Willingness to complete weekly surveys for 4 weeks after discharge. 3) Anticipated to need half or less of the usually prescribed amount of opioids based on the amount of opioids taken in the last 24 hours prior to the opioid medication being written for discharge (only patients who took 22.5 MME or less opioids in the last 24 hours prior to the day of discharge will be eligible for this study). Inclusion and exclusion criteria (including the amount of opioids taken in the last 24 hours prior to discharge) will be evaluated in the morning in patients scheduled to be discharged later that day.

Exclusion Criteria: 1) Patients under the age of 18 years, 2) Patients returning to institutional settings (e.g. prison, jail, mental health facility), 3) Pregnant women (patients will be approached after their C-section), 4) Decisionally challenged patients, 5) Blind or illiterate patients.

Based on our prior research factors such as emergency status, prior opioid use, repeat vs primary C-section, and associated procedures were not associated with post-discharge opioid use once we adjusted for last-24 hour inpatient opioid use. Hence, these patients will not be excluded.

We will perform a randomized clinical trial (RCT) of an EHR-based recommendation to prescribe opioids at discharge according to the recorded last 24-hour inpatient use according to current recommendations and evaluate its effect on the amount of opioids prescribed as well as pain control after discharge.

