We will seek a waiver of written consent for surveying providers who are given the dosing suggestion via the EHR-based Prescription Tool. At their convenience, these providers will complete an online postcard consent and survey via REDCap.

After consent, demographics and the best contact information will be collected (remotely by phone during the COVID-19 pandemic or as required by UCHealth) from those enrolled patients who indicate they are interested in completing the surveys after their hospital discharge.

We expect 44 patients to complete all four weekly surveys and we define the intent-to-treat sample as patients who complete one or more surveys (providing at least one observation to be used in analyses). To conservatively allow for increased variability due to attrition, 60 patients will be randomized equally electronically to intervention (prescription tool) or no intervention (prescription as usual). We will use an electronic randomization scheme created so that the principal investigator and statistician can remain blind to assignment.

At the time of writing the prescription for a patient the provider will be informed that a patient may be considered for a lower post-discharge opioid dose (No opioids for patients who did not take any opioids in the last 24 hours, and 10 oxycodone 5mg tablets, for patients having taken less than 22.5 MME, e.g. 1-3 oxycodone 5mg tablets in the last 24 hours). No dosing recommendations for patients having taken more than 22.5 MME will be made as these patients are not eligible for this study. Final dosing decisions and drug choices will remain at the discretion of the treating provider and decisions will be tracked.

For this pilot study, the provider information (best practice alert – BPA) will be operationalized via a written recommendation on paper handed to the provider by study staff in a sealed envelope or emailed with a read receipt that the provider will be asked to open and read. Alternatively, the BPA may be presented electronically using a screen. Providers will be asked to acknowledge that they read the BPA by closing the window or opening the envelope or email.

For the intervention group:

For patients receiving no opioids in the last 24 hours prior to an oxycodone or oxycodone/acetaminophen discharge prescription being written:

**BPA: “In the last 24 hours, your patient received NO opioids. Consider not prescribing any opioids for pain management after discharge.”**

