**F. Data Analysis Plan:**

The intent-to-treat (ITT) sample is defined as those who complete at least one survey. In our prior observational study, 100% of the C-section patients satisfied this criterion. If there is a subsample that does not complete at least one survey, we will compare that group to the ITT group on relevant demographic and clinical characteristics. Outcomes not requiring any response to the survey will be compared for all patients enrolled, regardless if they completed at least one survey.

The prescription tool and prescription as usual (PAU) groups will be compared on baseline demographic and clinical characteristics using Mann-Whitney tests, independent t-tests and chi-square tests as appropriate for continuous and categorical data; when necessary (i.e. when variables have distributions violating assumptions), nonparametric procedures will be substituted. We expect randomization to ensure group equivalence; should variables be different they will be evaluated as covariates in the analyses described below as appropriate.

Our primary analyses will compare the prescription tool group with the PAU group on oral morphine equivalent dose left over (not used) from the total amount of prescribed opioids. Based on our preliminary data, we will assume the control group to receive an opioid prescription for 20 oxycodone 5mg tablets (150MME), leading to a mean MME of 101.8 (SD 60.5) left over. Conservatively estimating a 50% adoption rate of the decision support tool by prescribing clinicians, we would expect a mean MME of 55 (SD 37.6) left over opioids in the intervention group. Assuming statistical comparisons will be made using Mann-Whitney test a sample size of n=22 per group (44 total using 1:1 allocation) will yield 90% power with an assumed one-tailed alpha of 0.05 (G-Power, version 3.1.9.2).

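### Randomisation is not stated to be stratified by the intake tier that selects the tool's message, and the primary test pools both tiers with no planned adjustment

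*Combined protocol and SAP*

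**What the plan says.** - **Two tiers.** Section III lists two suggested quantities for eligible patients. The first is "no opioids for home use for patients having taken no opioids in the last 24 hours prior to discharge". The second is 75 MME (10 oxycodone 5 mg tablets) for intake above zero and up to 22.5 MME. Section IV.C turns these into two separate provider messages.
- **When the tier can be known.** Section IV.B says that the eligibility criteria, including 24-hour intake, "will be evaluated in the morning in patients scheduled to be discharged later that day".
- **Prognostic value.** Section I presents in-hospital use over the last 24 hours as a strong guide to analgesic need at home. Section IV.B adds that several other factors were unrelated to post-discharge use once this one was adjusted for.
- **Allocation.** Section IV.C: "60 patients will be randomized equally electronically to intervention (prescription tool) or no intervention (prescription as usual". Neither strata nor blocks are mentioned.
- **Primary analysis.** Section IV.F compares whole arms on left-over MME, with a Mann-Whitney test assumed for sample size. It uses one control figure ("leading to a mean MME of 101.8 (SD 60.5) left over"), one intervention figure ("we would expect a mean MME of 55 (SD 37.6) left over opioids in the intervention group") and one adoption rate ("Conservatively estimating a 50% adoption rate of the decision support tool by prescribing clinicians"). None is split by tier.
- **Covariates.** Section IV.F compares baseline characteristics between arms and considers those that differ as covariates. For the mixed models it also requires a relation to the outcome.
- **By-tier results.** None are planned, although section IV.D says that the recommendation and the dose actually prescribed will be tracked.

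**The concern.** The tier does two jobs. It decides which message a tool-arm provider receives, and by the plan's own premise it predicts how much of a usual prescription goes unused in either arm. In a trial of 60, leaving such a variable to chance can produce a visible difference in tier mix between arms, and that difference then moves mean left-over MME whatever the tool does.

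The covariate rule is a weak remedy. It acts only after a difference has been seen, it does not say how large a difference counts, and the planned primary test takes no covariate.

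There is also a reporting loss. If extra prescriptions or worse pain appear in the tool arm, a pooled count cannot show which of the two messages they go with. Section IV.D would reassess the design if more than 5 intervention patients need prescriptions before scheduled follow-up, and sections IV.E and IV.G look ahead to a larger trial and a further grant application, so that distinction would be useful.

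**Working it through.** **1. The plan's own power figure.** Inputs from section IV.F: means 101.8 and 55, SDs 60.5 and 37.6, "a sample size of n=22 per group (44 total using 1:1 allocation", one-tailed alpha 0.05.
- Common SD = √((60.5² + 37.6²)/2) = 50.37; planned difference = 101.8 − 55 = 46.8; standardised difference = 46.8/50.37 = 0.929.
- Noncentral t with n multiplied by the Mann-Whitney efficiency 3/π gives 90.6% power. The plan says "will yield 90% power with an assumed one-tailed alpha of 0.05", so the figure reproduces. Nothing below disputes it.

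**2. How likely is a tier imbalance?** The documents do not give the tier mix, so I assume that 20-50% of patients are in the no-opioid tier. With 60 patients and exactly 30 per arm, the number K of such patients divides between arms as a hypergeometric variable.

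| No-opioid tier, K of 60 | P(arms differ by ≥4) | P(arms differ by ≥6) |
|---|---|---|
| 12 (20%) | 0.33 | 0.10 |
| 18 (30%) | 0.40 | 0.16 |
| 24 (40%) | 0.43 | 0.19 |
| 30 (50%) | 0.44 | 0.20 |

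A difference of 4 is 4/30 = 13 percentage points; 6 is 20 points. Treating the two arms as independent binomials instead gives 0.075-0.155 for 20 points or more at 30 per arm, which is the same picture.

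**3. Would the covariate rule notice?** Suppose that differing means p < 0.05 (an assumption; the plan does not say). Six-patient imbalances of 9 v 3, 12 v 6, 15 v 9 and 18 v 12 out of 30 give uncorrected chi-square p = 0.053, 0.091, 0.114 and 0.121. None is flagged. Some larger imbalances would be.

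**4. How far does the result move?** Extreme illustration, all of it assumed: 30% in the no-opioid tier (18 of 60), and these patients use none of a 150 MME prescription.
- Control, other tier: (101.8 − 0.3 × 150)/0.7 = 81.1 MME left over. Tier gap in control = 150 − 81.1 = 68.9.
- A 4-patient difference is an 11:7 split, so each arm is 2 patients from the balanced 9. The control mean shifts by 68.9 × 2/30 = 4.6 MME.
- With no tool effect, the other arm shifts by the same amount in the opposite direction. Between-arm shift = 2 × 4.6 = 9.2 MME (9.2/46.8 = 20%).
- With 50% adoption, the tool-arm mean in the no-opioid tier is 0.5 × 150 + 0.5 × 0 = 75. In the other tier, use is 150 − 81.1 = 68.9, so an adopted 75 MME prescription leaves 6.1 and the mean is 0.5 × 81.1 + 0.5 × 6.1 = 43.6 (equal use within the tier assumed). Tier gap = 75 − 43.6 = 31.4; shift = 31.4 × 2/30 = 2.1. Between-arm shift = 4.6 + 2.1 = 6.7 MME (6.7/46.8 = 14%).
- Scale: the standard error of the difference at 30 per arm is √((60.5² + 37.6²)/30) = 13.0 MME, so 6.7 is about half of one standard error.

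**5. A less extreme range.** If the tier gap is an assumed 15-45 MME, the same in both arms, a 20-point imbalance moves the difference by 0.2 × 15 = 3 to 0.2 × 45 = 9 MME (6-19% of 46.8).

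**The case against.** The best defence is that randomisation already deals with this. Chance imbalance causes no systematic error and does not inflate the type I error, and the stated power reproduces without stratification. That stands: the cost is precision and the interpretability of one result, not validity. A reader might infer that the comparison is biased; the documents do not support that.

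A reader might also infer that neither suggestion is evaluated. That goes too far. The hypothesis in section I concerns the tool as a whole, the pooled test answers it, and tracked recommendations and doses leave by-tier tabulation possible. What is missing is a plan to show the two messages separately. Formal by-tier tests would be weak in any case: at the overall effect size, one-tailed power is 37% with 5 per arm and 78% with 15.

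Three further points are fair:
- The documents are silent on stratification; they do not exclude it.
- The strong-guide statement is about 24-hour intake in general. Its strength within the narrow eligible band of 0 to 22.5 MME is not quantified, and zero left over in the no-opioid tier follows only where the provider adopts the suggestion.
- The covariate rule exists and offers partial protection, especially for the mixed models and covariate-adjusted secondary comparisons. It does not reach a plain Mann-Whitney primary test.

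**Conclusion.** The point holds as a modest, inexpensive design improvement. The variable that selects the message is available at enrolment and is, by the plan's own account, the main predictor of home use, yet no stratification by it is stated and the primary test has no planned adjustment for it. An imbalance of 4 or more no-opioid patients is fairly likely (0.33-0.44) and one of 6 or more is not rare (0.10-0.20), given an assumed 20-50% tier share. The consequence for one result is limited: about 7 MME at 50% adoption, or 9 MME with no tool effect, for a 4-patient difference on an assumption chosen to be extreme. The tier share, the tier gap and zero use in the no-opioid tier are assumptions, not document values.

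One qualification concerns the tier itself. Section IV.B describes the 24 hours both as those before the discharge prescription is written and as those before the day of discharge, with a morning check. The messages in section IV.C use the 24 hours before the prescription is written. A tier recorded in the morning may therefore not always match the message delivered.

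**What to change.** 1. State the randomisation method in section IV.C, and stratify the electronic list by tier as recorded at the morning eligibility check (0 MME; above 0 to 22.5 MME), with blocks within tier.
2. In section IV.F, make the primary test a tier-stratified rank test, for example van Elteren, whether or not the arms differ at baseline.
3. Tabulate prescribed MME, left-over MME, additional prescriptions and pain by tier and arm, labelled as descriptive only.
4. Reconcile the 24-hour windows in sections IV.B and IV.C, and report how often the stratum and the delivered message disagree.

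The cost is one binary stratum, a line of analysis text and one table from data already collected. The sample size and the content of the messages are unaffected. The small downside is that, if one tier is rare, its last block may be incomplete and its summaries imprecise.

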**BPA: “Consider prescribing the usual medications for pain management after discharge.”**

One week after hospital discharge interested patients will be contacted and asked to complete the first of four surveys. Participants will receive a \$10 gift card, or equivalent money order if requested, for each of four weekly surveys, for a total of \$40. All enrolled patients will complete the weekly post-discharge surveys within REDCap or by hard copy or phone if they do not have internet access.

Providers will not be paid to use the Prescription Tool or complete the short, one-time online survey.

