### I. Hypotheses and Specific Aims:

We have previously shown that 83% of patients after Cesarean section and 71% of thoracic surgery report taking half or less of opioids prescribed; 53% and 45% respectively report taking five or less of the prescribed pills. Such overprescribed opioids are stored in unsecured locations in the 75% of cases. These opioids represent a major source of potential morbidity and mortality. The *rationale* that underlies the proposed research is that once we have proven the efficacy of patient-centered pain management approaches, we can improve surgical pain therapy on a large scale.

**Specific Aim:** We will utilize the electronic health record to individualize pain therapy in surgical patients after hospital discharge using last 24-hour opioid intake as the decision variable for the amount of opioid pain pills prescribed. Our preliminary data indicate that current opioid prescription practice after surgery follows a “one size fits all” pattern. In-hospital opioid use 24 hours prior to discharge serves as a strong indicator to correctly estimate needs for analgesic medications at home. We will test our hypothesis that this tool will reduce the amount of opioid medications prescribed while maintaining patient post-operative pain control. We will test this tool prospectively for 44 post Cesarean section patients anticipated to use about half or less of the usually prescribed amount of opioid pain pills randomized equally to prescription tool intervention or no intervention (prescription as usual).

This protocol addresses only Specific Aim #3 of the original grant. Specific Aim #1 and #2 are addressed under a separate COMIRB protocol #14-1938.

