For patients receiving >0 MME up to ≤22.5 MME in the last 24 hours prior to an oxycodone or oxycodone/acetaminophen discharge prescription being written (example BPA is for 15 MME – 2 oxycodone 5mg tablets):

**BPA: “In the last 24 hours, your patient received opioid medication equivalent to 2 oxycodone 5 mg tablets by mouth. Consider writing for a total of 10 oxycodone 5 mg tablets for pain management after discharge.”**

Note, oxycodone-containing medications are the opioid prescribed in >96% of cases after Cesarean section at our hospital. We will make equivalent recommendations if hydrocodone is used. Based on our data, no other opioid medications have been prescribed for use after discharge following Cesarean section.

For the control group:

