**Uncommon Risks:**

- Tension or nervousness may occur from completing the study assessments. Participants can talk with the researchers about such problems, and can terminate the study if they wish.
- Problems with pain management. Only patients who are predicted to require approximately half or less than the usually prescribed opioid dose (i.e., those taking equal or less than 22.5 MME in the 24 hours prior to discharge) will be eligible. Patients will be randomized to have their provider receive a suggestion for a reduction of opioid dose versus standard of care. Providers may still choose to prescribe a higher dose as clinically indicated. The prescription tool will only make a suggestion. We will track the recommendation made as well as the actual dose prescribed.

We will follow up with all patients at half of their usual follow-up period (usually 2 weeks) via a REDCap survey, phone, email, or in clinic to assess how they are doing and if they are likely to run out of opioid medications despite still requiring them for acute surgical pain. For patients, who are running low on opioid pain medications, we will arrange for additional pain medications to be prescribed as deemed appropriate by their providers using the electronic prescription route if needed. We will monitor the study progress closely and reassess our study design

if more than 5 intervention group patients require prescriptions prior to scheduled clinic follow-up.

All patients are routinely given a phone number where they can reach a surgical provider 24 hours a day, seven days a week, in case pain therapy is inadequate.

The study team will monitor need for secondary prescriptions from providers to ensure that no significant under-prescription of opioid medications after surgery occurs.

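### Does sending control-arm providers a generic alert contradict the description of that arm as receiving no intervention?

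*Combined protocol and SAP*

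**What the plan says.** Section I says patients will be "randomized equally to prescription tool intervention or no intervention (prescription as usual"). The design text in section IV.C repeats this: "60 patients will be randomized equally electronically to intervention (prescription tool) or no intervention (prescription as usual").

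Section IV.C also describes how the provider alert (BPA) works. It is "operationalized via a written recommendation on paper handed to the provider by study staff in a sealed envelope", with email or a screen as alternatives, and "Providers will be asked to acknowledge that they read the BPA by closing the window or opening the envelope or email". These sentences come before the arm-specific headings and are not limited to one arm. Under "For the control group" the control alert then reads "Consider prescribing the usual medications for pain management after discharge".

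Elsewhere the comparator has other names. Section IV.B describes "a randomized clinical trial (RCT) of an EHR-based recommendation to prescribe opioids at discharge according to the recorded last 24-hour inpatient use" and names no comparator. The risk text in section IV.D says "Patients will be randomized to have their provider receive a suggestion for a reduction of opioid dose versus standard of care". Section IV.F, which defines the primary comparison, calls the control arm prescription as usual (PAU). No section states why control providers receive a message.

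**The concern.** A message from study staff at the moment of prescribing, which the provider is asked to acknowledge, is not literally nothing. Someone who read only the aims, the risk section or the analysis plan would picture unprompted care in the control arm.

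The message also acts on the decision that drives the primary outcome, since opioid left over depends on the amount prescribed. It could anchor providers to habit, or it could make them think about the prescription. The control planning mean comes from preliminary data, and nothing says those prescribers saw an alert. If the result were reported as tool versus no intervention, it would describe a contrast that the trial does not randomise. The pilot is meant to feed a later grant application, where tool versus no alert may be the contrast of interest.

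**Working it through.** **1. What the label means in context.** Both uses of the label pair each arm with a bracketed definition:

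| Place | Active arm | Control arm |
|---|---|---|
| I, and IV.C design text | prescription tool | no intervention, defined as prescription as usual |
| IV.C alert text | last-24-hour intake and a suggested amount (none, or a tablet count) | generic prompt toward usual medications |
| IV.D risk text | suggestion to reduce the dose | standard of care |
| IV.F analysis plan | prescription tool group | PAU group |

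The intervention is the prescription tool, so no intervention means care without the tool. The control alert fits that reading. It gives no 24-hour intake, drug, dose or tablet count, and it points to what the brackets already say. The analysis plan does not use the phrase no intervention at all.

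**2. Whether the sample size depends on the label.** The inputs are in section IV.F: mean left-over 101.8 MME (SD 60.5) in control and 55 MME (SD 37.6) with the tool, Mann-Whitney test, one-tailed alpha 0.05, 22 per group.

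- Difference: 101.8 − 55 = 46.8 MME.
- Pooled SD: √((60.5² + 37.6²)/2) = 50.37.
- Standardised difference: 46.8/50.37 = 0.929.
- Effective n per group for the Mann-Whitney test with a normal parent: 22 × 3/π = 21.0.
- Noncentrality: 0.929 × √(21.0/2) = 3.01, on 2 × 21.0 − 2 = 40 degrees of freedom.
- Power: 90.6%. With 21 per group it is 89.3%.

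The plan's 90% with 22 per group is reproduced. None of these inputs changes when the arm is renamed.

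**3. What an effect of the control message would do.** The documents give no figure, so the shifts below are assumptions. The control mean is moved, with both SDs and the tool arm held fixed:

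| Assumed shift in control mean (MME) | Power |
|---|---|
| −20 | 52% |
| −10 | 75% |
| 0 | 90.6% |
| +10 | 97% |
| +20 | over 99% |

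Power would be sensitive to a real shift. Renaming the arm, however, would not move any row of this table, and nothing in the documents supports one row over another. The planning mean assumes control patients receive a usual prescription (150 MME), and the control message asks providers to consider usual medications.

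**4. What the design gains and gives up.** Both arms' messages are labelled BPA, and the delivery text precedes the arm headings, so the natural reading is that both are delivered the same way. Any effect of merely being contacted is then largely shared by the arms, and the difference between them reflects the content of the recommendation. The cost is that the trial does not estimate tool versus unprompted care.

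**The case for a change.** The strongest case for a change is that the comparator is part of the trial's definition. Prescription as usual, standard of care and PAU all describe what the message asks for, and none reveals that a message is sent. The control text is not empty either. It points toward usual prescribing in patients selected because they are expected to need half or less of the usual amount. Section IV.E discusses provider education as a threat but says nothing about the control alert. A wording change would cost almost nothing.

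Part of this stands. The label in sections I and IV.C is imprecise, and the purpose of the control message is not given. The consequence does not follow. The message is disclosed word for word in the methods section, under its own heading, so anyone who writes up or appraises the trial from the methods will see what the control arm received. The documents contain no conclusion framed as tool versus no message, and section IV.G speaks of feasibility. The possible misreading lies in a future report, and the text needed to avoid it is already in the plan.

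**Conclusion.** The mismatch in wording is real but needs no change to the plan. It is a slip in terminology attached to a defensible design choice. Carried out as written, the plan gives a sound randomised comparison of a patient-specific recommendation with a generic usual-prescribing prompt, and an analyst would describe it that way from section IV.C. The label has no effect on allocation, the 22 per group, the 90% power or the analysis. Any effect of the control message itself has unknown size and sign, and may be zero.

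This rests on two readings: that the bracketed text defines the label, and that delivery and acknowledgement apply to both arms. Both are the natural readings of section IV.C, though the second is not stated outright.
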